5.3 Withdrawal Criteria

A patient must be withdrawn from the study if:

- the patient and/or his or her parent(s)/legal representative(s) withdraw(s) his or her assent/consent (defined as a patient and/or his or her parent(s)/legal representative(s) who explicitly take back his or her assent/consent); section [8.4](#) states how the patient's data will be handled
- the investigator considers it, for safety, lack of efficacy, and/or study compliance reasons, in the best interests of the patient that he or she be withdrawn

- the patient becomes pregnant
- the patient has a serum ALT or AST value >3 times the upper limit of the reference range and a serum total bilirubin value >2 times the upper limit of the reference range
- the patient has a serum ALT or AST value >5 times the upper limit of the reference range that is confirmed by testing <2 weeks later
- the patient has a QTcF interval >500 ms; the decision to withdraw a patient may be postponed until a repeat ECG is taken, if it is taken within 24 hours the patient is lost to follow-up (defined as a patient who fails to comply with scheduled study visits or contact, who has not actively withdrawn from the study, and for whom no alternative contact information is available [this implies that at least two documented attempts have been made to contact the patient])
- the patient and his or her parent(s)/legal representative(s) fails to comply with study procedures
- the patient attempts suicide or is at significant risk of suicide (either in the opinion of the Investigator or defined as a “yes” to suicidal ideation questions 4 or 5 or answering “yes” to suicidal behaviour on the C-SSRS during the study)

Patients who withdraw will not be replaced.

6 Investigational Medicinal Products

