17.8 Efficacy Analyses

17.8.1 General Efficacy Analysis Methodology

Change from Baseline Extension A in CDRS-R, CGI-S, BRIEF, CGAS, and PedsQL VAS using descriptive statistics by lead-in study and by lead-in treatment.

CGI-I score at Week 26 using descriptive statistics by lead-in study and by lead-in treatment.

Time to first loss of remission and time to first relapse will be analysed using Kaplan-Meier estimates.

For exploratory use a random effects slope and intercept model will be applied using Mixed Model Repeated Measurements (MMRM) to study long-term development in efficacy parameters such as CDRS-R.

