## **4 Analysis Sets**

The following analysis sets will be used to analyse and present the data:

- all-patients-treated set (APTS) – all patients who took at least one dose of vortioxetine in 12712A.
- full-analysis set (FAS) – all patients in the APTS with valid OLEXA assessment and at least one valid post-OLEXA assessment of the CDRS-R total score.

The safety analyses will be based on the APTS. The efficacy analyses will be based on the FAS.

The patients and data will be classified into the analysis sets according to the definitions above after the study database has been released.

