## 10.3 Analysis Methodology for the Secondary Endpoints

### 10.3.1 Analysis of the Secondary Endpoints

Absolute values and change from OLEXA in the continuous efficacy variables, except CGI-I, will be summarized descriptively. Absolute values of CGI-I will be summarized.

CDRS-R remission and relapse during treatment period will be summarized descriptively by visit.

For the continuous efficacy variables CDRS-R and CGI-S, change from OLEXA will be analyzed using a restricted maximum likelihood (REML)-based Mixed Model Repeated Measurements (MMRM) approach, using all available observations until completion or withdrawal.

The model will include country, lead-in study interacting with week as factors, and baseline score interacting with week as covariate. An unstructured covariance structure will be used to model the within-patient errors and the Kenward-Roger approximation will be used to estimate denominator degrees of freedom.

For the CDRS-R total score the primary analyses will be also presented by lead-in study by lead-in treatment.

In addition, ANCOVA models will be fitted for CDRS-R and CGI-S, including country and lead-in study as factors and baseline score as a covariate, the analysis will be conducted by visit, based on OC and LOCF.

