### **15 Sample Size Considerations**

No sample size calculation has been performed for the present study, which just includes patients who have completed the studies 12709A or 12710A and are eligible for enrolment for this study.

It is expected that some 15-20% of the 1200 patients randomised to the lead-in studies will drop out and that a maximum of 85% of these “lead-in completers” are expected to accept to continue into this extension study. This gives approximately 850 patients.

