## 17 Changes to Analyses Specified in the Protocol

The following changes have been made as compared to the latest version of the protocol:

- C-SSRS categorisation has been updated and will no longer include C-CASA.
- Treatment emergent adverse events (TEAE) in 12712A is defined as an adverse event that starts or increases in intensity or seriousness after visit 1 of study 12712A.
- The analyses regarding time to first relapse and time to first loss of remission have been removed
- The analysis of random slope and intercept has been removed

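### With the time-to-event analyses removed, remission and relapse are reported only by visit, with no denominator or withdrawal rule and no condition on OLEXA status for relapse

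*SAP*

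**What the plan says.** Protocol 16.2 lists time to first relapse (CDRS-R ≥40) and time to first loss of remission (CDRS-R >28) as secondary endpoints. Protocol 17.8.1 gives the method: "Time to first loss of remission and time to first relapse will be analysed using Kaplan-Meier estimates".

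SAP section 17 states: "The analyses regarding time to first relapse and time to first loss of remission have been removed". It gives no reason, and SAP 3.2 no longer lists either endpoint. In SAP Panel 2, remission (CDRS-R ≤28) and relapse (CDRS-R ≥40) remain as binary variables. Their analysis is one sentence in SAP 10.3.1: "CDRS-R remission and relapse during treatment period will be summarized descriptively by visit".

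Four other provisions bear on how that sentence would be carried out:

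- Efficacy analyses use the FAS, defined in SAP 4 as "all patients in the APTS with valid OLEXA assessment and at least one valid post-OLEXA assessment of the CDRS-R total score". A patient who leaves after one post-baseline score therefore belongs to it.
- In SAP 10.3.1, MMRM and the OC and LOCF ANCOVA are named for the CDRS-R and CGI-S scores only.
- Protocol 5.3 requires withdrawal when "the investigator considers it, for safety, lack of efficacy, and/or study compliance reasons" make it in the patient's best interest. Significant suicide risk is a further criterion. Under Protocol 8.4, collection then stops apart from the Withdrawal Visit and adverse event follow-up.
- SAP 18.4 assigns Withdrawal Visit scores to a target day. It also says that, before PA2, the CDRS-R was done only at Weeks 0, 12 and 26.

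**The concern.** The long-term effectiveness objective includes depressive symptoms, and readers will want to know what share of patients who were well at OLEXA stayed well. The plan no longer contains an analysis that answers this.

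There are three separate gaps. First, a percentage at each visit is a prevalence. It cannot be turned into the proportion who ever relapsed. Second, the relapse label is not tied to having been better beforehand. Protocol 5.2 sets no CDRS-R ceiling for entry, so patients can start the extension at 40 or above. Third, the SAP does not say what happens to a patient with no score at a visit. Because lack of efficacy is itself a ground for withdrawal, that choice can move the Week 26 remission figure.

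**Working it through.** **The plan's own figure.** SAP 15 expects that "15-20% of the 1200 patients randomised to the lead-in studies will drop out" and that at most 85% of completers continue; "This gives approximately 850 patients".

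- At 15% loss: 1200 × 0.85 × 0.85 = 867.
- At 17.5% loss: 1200 × 0.825 × 0.85 = 841.5.
- At 20% loss: 1200 × 0.80 × 0.85 = 816.

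So 850 lies inside the range. These are lead-in losses. Neither document gives an expected withdrawal rate for the 26-week extension or an expected remission or relapse rate ("No sample size calculation has been performed for the present study"). Every rate below is an assumption.

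**Step 1: what a by-visit relapse count records.**

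- At or above 40 at OLEXA and throughout: counted as relapsed at every visit, though never improved.
- Below 40 at OLEXA, at or above 40 at Week 8, below 40 again by Week 26: absent from the Week 26 relapse count.
- Below 40 at OLEXA, at or above 40 at Week 8, then withdrawn: counted at Week 8, with no stated treatment at Week 26.

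The same patient can also be counted at several visits, so adding visits does not give the number who ever relapsed. This step needs no assumed rate.

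**Step 2: Week 26 remission, if observed cases are used.** Let w be the share of the FAS withdrawn by Week 26, r_s the remission rate among those still assessed (stayers), and r_w the rate among those withdrawn.

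- All-FAS remission = (1 − w) × r_s + w × r_w
- Overstatement = r_s − all-FAS remission = w × (r_s − r_w)

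With r_s = 50%:

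| w | r_w = 50% | r_w = 25% | r_w = 0% |
|---|---|---|---|
| 15% | 0 | 0.15 × 25 = 3.75 points | 0.15 × 50 = 7.5 points (all-FAS 42.5%) |
| 30% | 0 | 0.30 × 25 = 7.5 points | 0.30 × 50 = 15 points (all-FAS 35%) |

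Over w = 10–40%, r_s = 50–70% and r_w from 0 to r_s, the range is 0 to 0.40 × 70 = 28 points. It turns negative if withdrawn patients do better than stayers.

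**Step 3: Week 26 relapse on observed cases.** Among patients below 40 at OLEXA, assume 20% ever relapse, half of these leave, one third of the remaining relapsers are back below 40 at Week 26, and 15% of non-relapsers leave.

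- Numerator: 0.20 × 0.5 × 2/3 = 0.0667
- Denominator: 0.20 × 0.5 + 0.80 × 0.85 = 0.78
- Week 26 figure: 0.0667 / 0.78 = 8.5%, against 20% who ever relapsed

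Now suppose 30% of all patients start at 40 or above, half of them are still there at Week 26, and 15% of them leave.

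- Numerator: 0.70 × 0.0667 + 0.30 × 0.5 × 0.85 = 0.174
- Denominator: 0.70 × 0.78 + 0.30 × 0.85 = 0.801
- Week 26 figure: 0.174 / 0.801 = 21.7%

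So the unconditioned figure can fall well below the cumulative 20% or rise above it.

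**The case against.** A reader might infer that the Week 26 percentages come only from patients who stayed, and so are known to be biased in the drug's favour. The SAP does not say that. It is silent on the denominator, and FAS N is possible. The non-missing denominator rule in SAP 12.2 covers other safety data. Observed cases is the natural default, since a patient without a score has no remission status, but it remains a default and not a stated rule.

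A reader might also infer that removing Kaplan-Meier creates the bias. It does not. The protocol stated no event rule for withdrawal, so a standard Kaplan-Meier estimate would censor a patient leaving for lack of efficacy and treat that censoring as non-informative. What the removal loses is the cumulative estimate. The protocol's relapse endpoint also had no condition on OLEXA status, so restoring it unchanged would leave that fault.

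Withdrawn patients do not simply vanish. The CDRS-R is scheduled at the Completion/Withdrawal visit, and the score can count at its assigned visit if it is within 7 days of the last dose (SAP 18.5.1). The assignment rules are in a Data Handling Plan that is not among the documents. SAP 6.2 reports withdrawals by reason, with Kaplan-Meier plots of time to withdrawal. These help a reader judge selection, but they are not linked to remission or relapse, and nothing stated carries a withdrawal score to Week 26.

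The removal is disclosed, the study's primary objective is safety, and Protocol 3.2 names the CDRS-R total score as the primary efficacy endpoint, which keeps MMRM, OC and LOCF analyses. All this stands and limits the weight of the point. Mean scores still do not say what share of patients stayed well.

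**Conclusion.** The point holds as a defect in supportive secondary outcomes. Two parts follow from the text alone: the plan yields no count of who ever relapsed, and its relapse percentage includes patients who never improved.

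The third part is conditional. If observed cases are used, Week 26 remission is likely to be too high, because lack of efficacy is a ground for withdrawal. At 50% remission among stayers and 15–30% withdrawal, the excess is 0 to 15 points. The top of that range requires that no withdrawn patient was in remission, so it is a worst case and not an expected value. For relapse no direction can be claimed.

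The documents do not support calling the Week 26 figures demonstrably biased, or calling maintained remission the main reading of effectiveness.

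**What to change.** 1. Keep the by-visit table, and state its denominator and how patients without a score are handled.
2. Show Week 26 remission on observed cases beside all FAS patients with withdrawals counted as not in remission. Label the second row as the conservative bound, since it errs the other way for patients who leave well.
3. Restrict relapse to patients below 40 at OLEXA, and loss of remission to patients at 28 or below at OLEXA.
4. For these two groups, report the Kaplan-Meier cumulative percentage with a first CDRS-R ≥40 and with a first CDRS-R >28. Add a sensitivity version that counts withdrawal for lack of efficacy as an event, stating whether primary or any recorded reason is used.
5. Patients seen before PA2 have post-baseline CDRS-R at Weeks 12 and 26 only, so their relapses are detected later or missed. Present them separately, or use only the Week 12 and 26 assessments for the pooled estimate.

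The cost is two extra tables from data already collected, and a less favourable remission figure beside the observed one.

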### **3.2 Secondary Endpoints**

Depressive symptoms:

- change from OLEXA to Week 26 in CDRS-R total score

Global Clinical Impression:

- change from OLEXA to Week 26 in CGI-S score
- CGI-I score at Week 26. The assessment of the CGI-I should be in reference to Baseline A in the lead-in studies. The Baseline A lies 12 weeks prior to OLEXA.

Cognitive function:

Children (7-11 years)

- change from OLEXA to Week 26 in BRIEF using the Global Executive Composite score
- change from OLEXA to Week 26 in BRIEF using the Metacognition Index

Adolescents (12-18 years)

- change from OLEXA to Week 26 in BRIEF-SR using the Global Executive Composite score
- change from OLEXA to Week 26 in BRIEF-SR using the Metacognition Index

Functionality:

- change from OLEXA to Week 26 in CGAS score
- change from OLEXA to Week 26 in PedsQL VAS

Palatability and acceptability:

- absolute value of palatability and acceptability item scores

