## **Appendix III**

### **SAS® Code**

## SAS® Code

### MMRM for analysing continuous endpoints

```
proc mixed noclprint data=xyz ic method=reml;  
  class usubjid country week lead-in _study;  
  model y=baseline country week lead-in_study*week baseline*week / s ddfm=kr;  
  repeated week/subject=usubjid type=un;  
  run;
```

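### Only CDRS-R and CGI-S get the MMRM; the cognitive and functional scales have descriptive Week 26 changes, exposed to dropout bias and with no planned 95% CI

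*SAP*

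**What the plan says.** SAP 3.2 gives the cognitive and functional endpoints the same form as the depression endpoint, for example "change from OLEXA to Week 26 in BRIEF using the Global Executive Composite score" and "change from OLEXA to Week 26 in CGAS score". The Metacognition Index, both BRIEF-SR scores and PedsQL VAS are worded alike. SAP Panel 2 types all of them as continuous, as it does CDRS-R and CGI-S.

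SAP 10.3.1 then has three layers:

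- All scales: "Absolute values and change from OLEXA in the continuous efficacy variables, except CGI-I, will be summarized descriptively".
- Two scales get the MMRM: "For the continuous efficacy variables CDRS-R and CGI-S, change from OLEXA will be analyzed using a restricted maximum likelihood".
- The same two get a further model: "In addition, ANCOVA models will be fitted for CDRS-R and CGI-S", of which the SAP says "the analysis will be conducted by visit, based on OC and LOCF".

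SAP 10.2 attaches 95% CIs to endpoints analysed inferentially. The default statistics in SAP 5 contain no CI. Appendix III heads its code "MMRM for analysing continuous endpoints", which sounds general, but 10.3.1 is the section that says which variables are modelled.

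On withdrawal, Protocol 5.3 requires it where "the investigator considers it, for safety, lack of efficacy, and/or study compliance reasons" make it best for the patient. Protocol 8.4 limits later data to the Withdrawal Visit and adverse event follow-up.

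**The concern.** Two of the four effectiveness objectives have no analysis that deals with missing visits. A patient who leaves early because the drug is not helping contributes to the early summaries of BRIEF, CGAS and PedsQL VAS but generally not to the Week 26 mean, which is the endpoint. SAP 10.2 bases the efficacy analyses on the FAS, and a patient enters the FAS with a valid OLEXA value and one valid later CDRS-R, available from Week 1. The other scales start at Week 4. The Week 26 mean can therefore describe a smaller, selected group, without an interval to show its precision. The repeated measurements needed for a model are already scheduled.

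**Working it through.** **1. Is the gap filled elsewhere?** SAP 18.2.1 and 18.3 deal with missing items within a form, not missing visits. SAP 18.4 assigns withdrawal assessments to a target day, so an early one does not reach Week 26. The last-assessment summary in SAP 12.2 is for safety data. Nothing else covers these scales.

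**2. The plan's own figure.** The only design number is about 850 patients (Protocol 17.12, SAP 15): 1200 randomised, 15-20% lead-in withdrawal, at most 85% continuing.

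- 1200 × 0.85 × 0.85 = 867
- 1200 × 0.80 × 0.85 = 816

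The stated 850 lies between these. The 15-20% belongs to the lead-in studies; no rate is given for the 26-week extension. I use it, and a wider range, as an assumption.

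**3. Bias identity.** Let d be the proportion missing at Week 26, S the mean change in stayers and L the mean change that leavers would have had. The full mean is (1 − d)S + dL, so the observed mean is off by S − [(1 − d)S + dL] = d(S − L). Suppose leavers do 0.5 SD worse (assumed):

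| d | n at Week 26 = 850(1 − d) | bias = 0.5d |
|---|---|---|
| 10% | 765 | 0.05 SD |
| 20% | 680 | 0.10 SD |
| 30% | 595 | 0.15 SD |
| 40% | 510 | 0.20 SD |

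For scale, a 95% CI on a mean of 680 patients has half-width 1.96/√680 = 0.075 SD. BRIEF and BRIEF-SR each cover only part of the sample, so theirs would be wider.

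**4. What a likelihood model does.** Illustrative simulation: 850 patients; Weeks 4, 8, 12, 18 and 26; SD of change 1; true Week 26 change −0.50 (negative is improvement); dropout depending on the last observed change (logit slope 0.8 per SD). The model is unstructured maximum likelihood, in effect an MMRM without covariates.

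| dropout by Week 26 | observed cases | LOCF | likelihood model |
|---|---|---|---|
| 7.9% | −0.535 | −0.459 | −0.497 |
| 18.5% | −0.589 | −0.417 | −0.502 |
| 31.5% | −0.650 | −0.354 | −0.494 |
| 44.7% | −0.723 | −0.308 | −0.500 |

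At 18.5% dropout observed cases err by 0.589 − 0.500 = 0.089 SD in the favourable direction. LOCF errs by 0.500 − 0.417 = 0.083 SD in the other. The likelihood model is within 0.01 SD throughout.

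**5. Sensitivity to the dropout mechanism** (slopes 0.3-1.0 per SD):

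- Dropout on the scale's own change: 0.029-0.095 SD too favourable at 15% and 0.039-0.126 SD at 20%. A second set-up gave 0.02-0.10 SD over 15-20%.
- Dropout on a depression score correlated 0.3-0.7 with the scale: about 0.01-0.07 SD too favourable at 15-20%.
- Dropout on current level rather than change: 0.009-0.028 SD understated at 20%.

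The range over the first two mechanisms is about 0.01-0.13 SD, and the third reverses the sign.

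**6. Can the model be copied unchanged?** SAP 10.3.1 includes lead-in study by week. The BRIEF form follows age at OLEXA. Only 12710A is described as having patients who turned 18 (Protocol 3.1), which suggests that lead-in study and age group nearly coincide. Within one BRIEF form the term may then rest on very few patients or be inestimable. CGAS and PedsQL VAS are collected at all ages and do not have this problem.

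**The case against.** The strongest reply is that the SAP keeps to the protocol. Protocol 17.8.1 plans descriptive statistics for all five scales, with a random-slope model for exploratory use only. SAP 17 removes that model, and 10.3.1 adds modelling for two scales. A reader might infer that a commitment for BRIEF, CGAS or PedsQL VAS was broken. None was. The point is an improvement, not a correction.

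A reader might also infer that these changes cannot be compared with CDRS-R in the same report. The documents do not support that: CDRS-R and CGI-S also get the descriptive summary and an observed-case ANCOVA, so a like-for-like comparison is planned.

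Nor is the missing LOCF analysis a defect. In the simulation LOCF erred about as much as observed cases, in the opposite direction.

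Attrition will be visible. SAP 5 reports n, and SAP 6.2 gives reasons for withdrawal and Kaplan-Meier plots. Late withdrawers with an assessment may be windowed to Week 26; the rules are in the Data Handling Plan, which is not among the documents. It is also fair that lack-of-efficacy withdrawal is probably led by depressive symptoms, which shrinks the bias on the other scales.

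These replies limit the importance of the point. They do not supply a Week 26 estimate that allows for dropout, or an interval. Showing n does not tell the reader how large the bias is or which way it runs.

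**Conclusion.** The point holds as a low-cost improvement. Six variables carrying two effectiveness objectives have only a descriptive Week 26 change, in patients with a Week 26 or windowed assessment, with no planned 95% CI. That these are in effect observed cases is an inference: 10.3.1 does not use the label for these scales, but names no model or imputation for them.

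Size and direction are not known from the documents. It would be tempting to state one percentage by which the gain is overstated. That would need a true gain, SDs, an extension withdrawal rate and a dropout mechanism, none of which the documents supply, and the sign can change.

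The model's advantage rests on missingness at random given the scale's earlier values. If withdrawal depends on something those values do not carry, the model may reduce the bias without removing it.

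The study is open-label and uncontrolled, and its primary objective is safety. No test, power calculation or decision rule uses these scales, and an unbiased mean still could not separate drug effect from natural course.

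**What to change.** In SAP 10.3.1, extend the MMRM to six variables: BRIEF GEC and MI, BRIEF-SR GEC and MI, CGAS, and PedsQL VAS total.

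- Use Weeks 4, 8, 12, 18 and 26, and report the Week 26 estimate with 95% CI and n per visit. The Appendix III code prints fixed-effect solutions only, so add a statement that produces this estimate.
- Fit BRIEF and BRIEF-SR separately. Where lead-in study by week is not estimable within the age form, drop that term and keep week as a factor.
- Keep the by-visit descriptives. Do not add LOCF.
- If the sponsor prefers descriptive results only, say why and label them observed-case.

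The cost is SAP wording and a little more programming; no new data are needed. One limit remains: FAS patients with no post-OLEXA value on a scale, such as those leaving before Week 4 without a withdrawal assessment, still do not contribute.

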# 2 Study Design

This is an interventional, multi-national, multi-site, open-label, flexible-dose, long-term extension study in child and adolescent patients with MDD who completed one of the double-blind, placebo-controlled, active-reference studies 12709A and 12710A.

The Baseline Visit, hereafter referred to as OLEXA, of this extension study, will be Visit 12 (Completion Visit) of lead-in Study 12709A or 12710A, see section 18.1.

The dosage of vortioxetine will be initiated at 5 mg/day for the first 2 days prior to receiving 10 mg/day. The target dose is 10 mg/day; however, the investigator has the possibility to adjust the dose in case of unsatisfactory response up to 20 mg or in case of dose-limiting adverse events. The dose can be up or down titrated with 5 mg/day. The patient should receive the same dose for 2 days before being up-titrated to a new dose. Changes in dosing may occur at any site visit during the treatment course at the investigator's discretion but the maximum dose may not exceed 20 mg/day.

[figure not shown]
For subset of patients participating in the palatability assessment (patients enrolled in Bulgaria, Estonia, Germany, Latvia, Mexico, Poland, Russia, Serbia, Ukraine, and Colombia), palatability and acceptability of vortioxetine oral drops will be assessed after intake of a single dose (5-20 mg) corresponding to the patient's current vortioxetine dose (instead of their vortioxetine tablet on that day). The assessment can be done at any visit to the clinic from Week 4 to Week 18 (i.e., at Visits 5, 7, 9, or 11).

The treatment period is 26 weeks. The total study duration per patient from OLEXA to the end of follow-up will be approximately 30 weeks.

If possible, patients who withdraw are to be seen for a withdrawal visit as soon as possible and they will be contacted for a safety follow-up visit 4 weeks after withdrawal.

The study design is presented in [Panel 1](#).

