## 10.2 General Efficacy Analysis Methodology

Unless otherwise specified, all the efficacy analyses will be based on the FAS.

All the tables and graphs will be presented for all patients and by lead-in studies and by lead-in treatments, respectively.

Analysis of the endpoints subjected to inferential statistical methods will be presented with 95% CIs.

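### With OLEXA score as a fixed covariate in a single-treatment study, the model-based 95% CIs for mean change from OLEXA are too narrow for the population mean change

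*SAP*

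**What the plan says.** - **Design (SAP 2):** "This is an interventional, multi-national, multi-site, open-label, flexible-dose, long-term extension study in child and adolescent patients with MDD". There is no concurrent comparator.
- **Endpoint (SAP 3.2):** "change from OLEXA to Week 26 in CDRS-R total score"; CGI-S is handled in the same way.
- **MMRM (SAP 10.3.1):** "The model will include country, lead-in study interacting with week as factors, and baseline score interacting with week as covariate", with an unstructured covariance, and "the Kenward-Roger approximation will be used to estimate denominator degrees of freedom".
- **MMRM code (SAP Appendix III):** "model y=baseline country week lead-in_study*week baseline*week / s ddfm=kr". OLEXA score appears only on the right-hand side. The code has no LSMEANS or ESTIMATE statement, so neither the baseline value nor the country and study weights of the reported mean are fixed.
- **ANCOVA (SAP 10.3.1):** "In addition, ANCOVA models will be fitted for CDRS-R and CGI-S, including country and lead-in study as factors and baseline score as a covariate". These are run by visit, on OC and LOCF data.
- **Intervals (SAP 10.2):** "Analysis of the endpoints subjected to inferential statistical methods will be presented with 95% CIs".

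The SAP also plans descriptive summaries of change from OLEXA (n, mean, SD and so on), overall and by lead-in study and lead-in treatment.

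**The concern.** Baseline-adjusted MMRM and ANCOVA are built to compare arms. In a between-arm contrast with a common slope, the error in the estimated mean baseline is shared and cancels. Here the quantity reported is the mean change itself, and OLEXA score is half of every change score. Treating it as a fixed regressor, and evaluating at its observed mean, treats that mean as known.

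The CIs on CDRS-R and CGI-S change are the only model-based efficacy intervals in the SAP. A reader will take them as intervals for the mean change in patients like these. On that reading they overstate how precisely the change is known. A larger sample does not cure this: both the counted and the omitted variance fall as 1/n, so the coverage shortfall stays the same.

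**Working it through.** **Inputs from the documents.** Confidence level 95% (taken as two-sided) and planned size: "This gives approximately 850 patients". That figure reproduces: 1200 × (1 − d) × 0.85 gives 867 for d = 15%, 841.5 for d = 17.5% and 816 for d = 20%, so about 850 is fair. It is the only computed figure available; no precision or CI width is stated.

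**Inputs assumed.** The documents give no SDs, correlation or dropout rate within 12712A. Assumed for CDRS-R: SD at OLEXA (SDx) and at Week 26 (SDy) between 11 and 13, correlation ρ between 0.3 and 0.7.

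**Formulae** (change = Y − X, patient-weighted mean, complete data):

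- slope of change on baseline: b = ρ·SDy/SDx − 1
- variance counted by the model: V_res = SDy²(1 − ρ²)
- variance omitted: b²·SDx²
- correct variance: V_tot = V_res + b²·SDx² = SDx² + SDy² − 2ρ·SDx·SDy
- SE ratio: R = √(V_res/V_tot)
- coverage of the population mean change: 2Φ(1.96·R) − 1
- half-width: 1.96·√(V/n)

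**Worked case, SDx = 13, SDy = 11, ρ = 0.3.** b = 0.3 × 11/13 − 1 = −0.746. V_res = 121 × 0.91 = 110.1. Omitted = 0.746² × 169 ≈ 94.1. V_tot = 204.2. R = √(110.1/204.2) = 0.734. Coverage = 2Φ(1.439) − 1 = 85.0%. Half-width at n=850: 0.71 reported against 0.96 correct, a gap of 0.26 from unrounded values.

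| SDx | SDy | ρ | V_res | V_tot | SE ratio | Coverage | Half-width, n=850: reported / correct |
|---|---|---|---|---|---|---|---|
| 13 | 11 | 0.3 | 110.1 | 204.2 | 0.73 | 85.0% | 0.71 / 0.96 |
| 13 | 11 | 0.45 | 96.5 | 161.3 | 0.77 | 87.0% | 0.66 / 0.85 |
| 12 | 12 | 0.3 | 131.0 | 201.6 | 0.81 | 88.6% | 0.77 / 0.95 |
| 12 | 12 | 0.5 | 108.0 | 144.0 | 0.87 | 91.0% | 0.70 / 0.81 |
| 12 | 12 | 0.7 | 73.4 | 86.4 | 0.92 | 92.9% | 0.58 / 0.62 |
| 11 | 13 | 0.7 | 86.2 | 89.8 | 0.98 | 94.5% | 0.62 / 0.64 |

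The first and last rows are the extremes of the assumed grid. The required widening is 1/R, from 1/0.980 = 1.02 to 1/0.734 = 1.36.

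**Simulation, n=850.**

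- ANCOVA, equal SDs, 14 assumed countries, patient-weighted means: coverage about 87-88% at ρ = 0.2, 90-91% at 0.5 and 92-93% at 0.7. The plain mean change with SD/√n covered 94.5-95.3%.
- The same ANCOVA intervals, judged against the mean change conditional on the observed mean baseline, covered 94.6-95.2%.
- MMRM with unstructured covariance and about 22% dropout depending on earlier scores: about 87-93% over ρ = 0.2-0.7 (300 runs per setting, Monte Carlo error 1.5-2 points).
- SDs 13/11, ρ = 0.45: 87.9% patient-weighted, 90.8% with equal country weights, 95.1% for the paired change.

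Kenward-Roger does not repair this. It allows for estimated covariance parameters, not for a sampled baseline mean.

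**Subgroups.** With an assumed 140 patients fitted alone, SD 12 and ρ = 0.3-0.5, the half-width gap is 1.96 × (√(201.6/140) − √(131.0/140)) = 0.46 down to 1.96 × (√(144/140) − √(108/140)) = 0.27 points.

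**The case against.** **Conditional inference is the ordinary regression reading.** Given the observed baselines, the intervals are nominal, and the SAP names neither the target nor the evaluation point. The first part is true. But the stated endpoint is simply change from OLEXA, and nothing in the SAP limits it to the observed baselines. If a conditional target is meant, the SAP has to say so.

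**Country weighting matters.** A reader might infer that the adjusted mean must equal the raw mean change and that its SE must fall below SD(change)/√n. Neither follows for this model, because it also contains country and lead-in study. With equal country weights and 14 assumed countries sized in proportion to 1/rank, the variance inflation is about 1.74. In the 13/11, ρ = 0.45 case the reported SE is then √(1.74 × 96.5/161.3) = 1.02 times SD/√n. Coverage is still short: √(167.9/(167.9 + 64.8)) = 0.85, giving about 90%. The omission remains in a wider interval.

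**The unconditional answer is already available.** The planned descriptive tables give n, mean and SD of change, so an interval can be formed for observed cases. This limits the harm but does not correct the model-based intervals that will be presented.

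**Materiality is low.** These are secondary efficacy endpoints in a safety study, and no test, margin or decision rule uses the intervals. At n=850 the gap is at most about 0.26 points on a scale running from 17 to 113. This stands, and it bounds the importance of the point.

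**Conclusion.** The point holds for the population mean change when the mean is evaluated at the observed mean baseline. The model-based SE then omits b²·Var(baseline)/n and the 95% CI is too narrow. Under assumed CDRS-R SDs of 11-13 and a correlation of 0.3-0.7, the SE is 0.73-0.98 of the correct one and coverage is about 85-94.5% with patient-weighted means, somewhat closer to 95% with equal country weights. The missing half-width is about 0.01-0.26 points at n=850 and larger in lead-in subgroups. The mechanism applies equally to CGI-S, but no size is given for it because the documents supply no SDs or correlation.

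Two stronger readings are not supported. A reader might quote one coverage figure as a property of the plan; coverage depends on the SD ratio, the correlation and the weights, none of which the documents give. A reader might also conclude that comparisons between lead-in groups are compromised; the shared baseline mean cancels there, so they are not materially affected.

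**What to change.** **MMRM.** Include OLEXA as week 0 in the response vector and remove baseline and baseline*week:

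- response: score at weeks 0, 1, 2, 4, 8, 12, 18 and 26
- fixed effects: country, week, lead-in_study*week
- repeated week within patient, unstructured covariance, Kenward-Roger as planned
- report week t minus week 0 with its 95% CI, by lead-in study and overall
- state that the overall contrast weights the two lead-in studies by their observed proportions; otherwise it depends on an unstated choice

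This fits the existing plan. The SAP's FAS already requires a valid OLEXA CDRS-R, and SAP 18.4 notes that week 0 was assessed even before the second amendment added visits. Because country has no interaction with week, its effect cancels from week t minus week 0, which removes the country-weighting question.

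**By-visit ANCOVA tables.** Report mean change with SD(change)/√n, or keep the models and label their CIs as conditional on the observed baseline.

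**Cost.** SAP wording and a few lines of code. The unstructured matrix for CDRS-R grows from 7 to 8 time points (28 to 36 parameters). CIs become about 2-36% wider under the assumptions above.
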